Secondary objectives of this study include determining 2-year regional control, progression-free survival, metastasis-free survival, and overall survival. Differences between intensity-modulated radiation therapy and proton therapy with respect to disease-related outcome and toxicity/QOL will also serve as secondary objectives.

Background, Preliminary Data, and Significance

Standard options for advanced-stage, HPV+, oropharyngeal cancer include either definitive chemoradiation or surgery followed by adjuvant radiation (+/- chemotherapy). The approach using TORS for the primary tumor resection followed by staged SND and adjuvant RT to the primary tumor bed and bilateral neck nodes has been pioneered at the University of Pennsylvania (1, 2). Disease outcomes are generally favorable, with overall survival of 90% (3), and locoregional control of 95–100% with either organ preservation RT (4), or with the TORS-based approach (5, 6); however, treatment-related morbidity can be significant. Definitive chemoradiation can result in long-term feeding tube use in up to 20% of patients (7), while 1 out of 4 patients who receive post-op RT after TORS resection experience ulceration and tissue breakdown at the primary resection bed as a late consequential effect of severe, acute mucositis (8). Approaches to decrease toxicities are therefore warranted.

One potential approach may be to omit post-op RT to the primary resection bed. A study from our group of 30 patients with oropharynx cancer (T1-2 in 83%) treated with surgery alone (TORS + SND) who refused adjuvant RT revealed a local control of 97% with surgery alone (9), calling into question the need to radiate the primary tumor bed in such patients. We will therefore conduct a pilot study of TORS alone to the primary tumor and SND followed by adjuvant RT (+/- Chemotherapy) to the regional nodes. The decision to add concurrent chemotherapy to postoperative radiation will be based on current standards of care, which recommend the addition of chemotherapy for the presence of either nodal extracapsular extension or positive margins (10). Margin positivity is an exclusion criterion for this study; therefore, the only indication for concurrent chemotherapy for this phase II study would be for nodal extracapsular extension.

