3.1 General Design

This is a single-arm phase II study of post-op RT in the setting of locally-advanced HPV(+) oropharynx cancer. Only patients with small volume primary site disease (T1 or T2), resected with negative margins (2 mm or greater), without PNI, will be eligible.

- Patients will undergo post-op RT (+/- chemotherapy) to 60-66 Gy, per established clinical guidelines (10-12)
- P16 positivity via immunohistochemistry will be used as a surrogate for HPV positivity (standard of care practice at Penn)
- Regional nodes will be included in the RT field, as per current practice standards
- The primary tumor bed will be excluded from the RT field
- Platinum-based chemotherapy will be required for patients with evidence of extracapsular extension, based on current clinical guidelines (10-12)

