5.4 Study Visit Schedule

Please see above in section 5.1. Patients will be followed on study for a period of approximately 2 years after completion of RT, after which time, routine follow-up will continue “off-study” per the discretion of the treating physicians. Patients will be followed for short and long term RT-associated toxicity and local and /or regional recurrence.

6 Statistical Plan

Study design

A total of 60 patients will be accrued over a total of 1.0 year. Patients will be followed on study for a period of approximately 2 years after completion of RT. After this time, patients will continue to be seen in follow-up by their treating physicians, per physician discretion according to physician and institutional practices.

Patients will be enrolled into two non-randomized treatment strata: IMRT (photon) and PBRT (proton). We anticipate enrolling approximately 30 subjects in each stratum given our recent experience with patterns of insurance approval for PBRT versus IMRT (please see rationale described above in the introduction regarding IMRT vs. PBRT. Patients will not be randomized to IMRT vs. PBRT, but rather the decision to treat with one modality versus another is based on insurance carrier approval status. .

Data analysis plan

The primary objectives of the study are to estimate the 2-year local (primary site) control rate at the primary tumor site, and 2-year rates of RT-associated toxicities (as measured by CTCAE, version 4.0 and patient-reported QOL). We will estimate the distributions of time of loss of local control and time to RT-associated toxicity by exact 95% confidence intervals. We will compare the distributions of time to local recurrence and time to toxicity between strata by the logrank test.

Secondary objectives include determining 2-year regional control, progression-free survival (PFS), metastasis-free survival (MFS), and overall survival (OS). Differences between intensity-modulated radiation therapy and proton therapy with respect to disease-related outcomes and toxicity/HRQoL will also serve as secondary objectives. We will summarize data on regional control, PFS, MFS and OS using Kaplan-Meier curves; estimate proportions of toxicities by 95% exact confidence intervals; and make comparisons between treatment strata by the logrank test.

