HRQoL evaluations will be obtained at baseline and completion of RT, and then approximately at 3, 6, 12, 18 and 24 months after completion of RT. We will estimate mixed linear models predicting HRQoL from treatment stratum, demographic and baseline clinical criteria. It is necessary to adjust for these factors to reduce potential confounding bias, as the treatments will not be randomized.

Sample size justification

With 30 patients per stratum, we will have 78% power to detect a difference in failure of 2-year local control, assuming a null rate of 5% and an alternative rate of 17.5%, using a one-tailed exact binomial test with type I error rate 10%.

Also with 30 patients per stratum, we will have 90% power to detect a difference in stratum means of HRQoL outcomes, provided that the effect size (absolute difference in means divided by common standard deviation) is larger than 0.86. This calculation assumes a two-tailed Student *t* test with type I error rate 5%.

Given that the decision to treat with IMRT vs PBRT is not randomized, but rather based on current insurance approval/denial patterns, we expect there to be an approximate 1:1 ratio of IMRT:PBRT; however, this study will not obligate 1:1 IMRT:PBRT. The comparison of IMRT to PBRT is a secondary objective of the study, and inability to populate the strata in a 1:1 ratio will not impede evaluation of the data for the primary objective. If recruitment goals are not met for each stratum, adjustments will be made to the data analysis as it pertains to the secondary objective of comparing IMRT to PBRT.

Interim analysis

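### The IMRT v PBRT comparison of time to CTCAE toxicity is an unadjusted logrank test, although the plan calls adjustment necessary for HRQoL in the same non-randomized strata

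*Combined protocol and SAP*

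**What the plan says.** Patients enter two non-randomized strata, IMRT and PBRT, with about 30 expected in each (section 6, Study design). The Data analysis plan then gives these methods for comparing them:

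- For local recurrence and toxicity: "We will compare the distributions of time to local recurrence and time to toxicity between strata by the logrank test".
- For the secondary outcomes it will "make comparisons between treatment strata by the logrank test".
- For HRQoL: "We will estimate mixed linear models predicting HRQoL from treatment stratum, demographic and baseline clinical criteria". The reason follows: "It is necessary to adjust for these factors to reduce potential confounding bias, as the treatments will not be randomized".

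One other sentence, under Sample size justification, mentions a change to the analysis: "If recruitment goals are not met for each stratum, adjustments will be made to the data analysis". It is triggered by a recruitment shortfall, not by confounding. The synopsis says the analysis is stratified by type of RT, but that only defines the groups being compared.

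The toxicity difference between modalities is a stated secondary objective (2.2.2) and endpoint (3.3). The Background section says that insurance approval, not clinical features, decides the modality.

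**The concern.** The plan gives a general reason for adjusting, that treatment is not randomized, and applies it to one of two parallel outcomes. The patients, strata and allocation process are the same for both. The patient-reported side of toxicity is already covered by the HRQoL models, so the gap concerns time to CTCAE toxicity.

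If a factor that affects toxicity differs between the strata, part of the CTCAE difference will reflect that factor. The HRQoL result would be protected against this and the CTCAE result would not. CTCAE grades and HRQoL scores measure different things and can disagree for good reasons. Unequal adjustment adds an avoidable further explanation, and it leaves the choice between adjusted and unadjusted toxicity results open until the data are seen.

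**Working it through.** **1. Figures in the plan.** No power, event count or effect size is stated for the toxicity comparison, so there is no figure to reproduce for it. The neighbouring figures do reproduce:

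- Local control: exact binomial, n = 30 ("assuming a null rate of 5% and an alternative rate of 17.5" per cent). Rejecting at 4 or more failures gives type I error 0.061 and power 0.795, against the stated 78%.
- HRQoL: t test, 30 v 30, effect size 0.86, df = 58, noncentrality 0.86 × √15 = 3.33. Power is 0.906, against the stated 90%.
- Null hazard: −ln(0.95)/24 = 0.00214 per month, as stated.

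Neither power figure depends on how the toxicity comparison is adjusted.

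**2. How imbalance becomes an apparent effect.** Extracapsular extension (ECE) serves as an example factor because it brings chemotherapy with it: "Platinum-based chemotherapy will be required for patients with evidence of extracapsular extension". The Background adds that "the only indication for concurrent chemotherapy for this phase II study would be for nodal extracapsular extension". One ECE term can therefore stand for both.

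Assumptions not in the documents: 24-month toxicity risk 25% without chemotherapy (range 10-40%), chemotherapy hazard ratio (HR) 2 or 3, and no modality effect. The risk with chemotherapy is then 1 − 0.75² = 43.8% or 1 − 0.75³ = 57.8%. With half the patients having ECE, expected events are 30 × 0.25 + 30 × 0.438 = 20.6, or 30 × 0.25 + 30 × 0.578 = 24.8.

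The spurious risk difference between strata is the gap in factor prevalence times the gap in risk:

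- 40% v 60%: 0.20 × 18.8 = 3.8 points (HR 2); 0.20 × 32.8 = 6.6 points (HR 3).
- 30% v 70%: 0.40 × 18.8 = 7.5 points (HR 2); 0.40 × 32.8 = 13.1 points (HR 3).

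**3. False-positive rate by simulation.** 30 v 30, exponential times, censoring at 24 months, two-sided 5% tests. There were 8,000 trials per scenario for the logrank and 6,000 for the Cox likelihood-ratio test (modality, ECE, age). The Monte Carlo standard error near 5% is √(0.05 × 0.95/8,000) = 0.24 points and √(0.05 × 0.95/6,000) = 0.28 points.

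| ECE in the two strata | Logrank, HR 2 / HR 3 | Logrank over 10-40% toxicity | Cox, HR 2 / HR 3 |
|---|---|---|---|
| Unrelated to modality | 5.1% / 5.0% | 4.7-5.7% | 5.6% / 5.5% |
| 40% v 60% | 5.6% / 6.8% | 5.5-7.8% | 5.9% / 5.5% |
| 30% v 70% | 8.5% / 16.2% | 6.8-22.4% | 5.2% / 5.7% |

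Placing events at the six toxicity visits changes little (5.0/4.8%, 5.9/7.0%, 8.9/16.8%). Drawing each patient's ECE status at random, instead of fixing the split, gives 6.4-8.2% at 40 v 60. A separate run with random draws and 30% baseline toxicity gives 6.5/9.2% at 40 v 60 and 10.3/20.1% at 30 v 70. A logrank stratified on the factor stays at 4.6-5.4% in that run.

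**4. How likely is the imbalance?** If ECE is unrelated to modality, exact binomial calculation with 30 v 30 gives a gap of at least 20 points in 12.0% of trials (prevalence 30%) to 15.5% (prevalence 50%). A gap of at least 40 points arises in 0.1-0.3%.

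**5. A demographic example.** Take ECE as unrelated, chemotherapy HR 2, and mean age differing between strata. These inputs are also assumed.

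| Age difference, HR per SD | Unadjusted | Stratified by ECE only | Cox with age |
|---|---|---|---|
| 0.3 SD, 1.5 | 5.5% | 5.8% | 5.7% |
| 0.5 SD, 1.5 | 7.4% | 7.5% | 5.9% |
| 0.5 SD, 2 | 11.6% | 11.8% | 5.9% |

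Stratifying on ECE alone does nothing for a demographic factor.

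**6. Price of adjusting.** With ECE split 30 v 70 but not prognostic, power moves from 33.8% to 30.6% (modality HR 2), 20.6% to 19.7% (HR 0.5) and 38.8% to 35.9% (HR 0.33). That is a loss of about 1-3 points. A Wald test at about 10 events loses far more (39.0% to 22.5% at HR 0.33), so the choice of test matters.

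**The case against.** The strongest reply is that insurance, not clinical features, decides the modality. On that description ECE is a weak candidate for confounding, and the logrank holds about 5%. No document links insurance to any prognostic factor. In the moderate cases the adjusted test is not visibly better: most differences there lie within simulation error, and the likelihood-ratio test runs slightly high (5.2-5.9% at 21-25 events, 6.4% at about 9). Toxicity is given no grade or event type in section 6, so neither the event count nor the number of model terms it can carry is known. The comparison is secondary and its power is low on these assumptions (about 20-48%).

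All of this stands as a limit on size, and it makes any particular covariate list or event threshold a matter of judgement. It does not remove the inconsistency. Section 6 restates the insurance mechanism and still calls adjustment necessary. Its adjustment list also includes demographic factors, which a statement about clinical features does not address.

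A reader might infer that the toxicity comparison is biased, or that the unadjusted test would hide a real difference. The documents show neither. No imbalance is reported. With ECE unrelated to modality and a modality HR of 0.5, power is 26.0% unadjusted v 27.7% adjusted (chemotherapy HR 2) and 29.9% v 33.4% (HR 3), which is too small a gap to call masking.

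**Conclusion.** The point holds as an inconsistency of method on a stated secondary objective: the plan's own reason for adjusting HRQoL applies to time to CTCAE toxicity, and the stated test does not follow it. The size and direction of any bias are unknown. On the assumptions above, the false-positive rate is about 5% without imbalance, about 6-7% at a fixed 40 v 60 split and about 9-16% at 30 v 70, where baseline toxicity is 25% and the factor's HR is 2 to 3. The 30 v 70 case is extreme and would rarely arise by chance.

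It would go too far to conclude that the primary results are compromised. The single-arm estimates of local control and toxicity involve no comparison of modalities, and the stated power figures stand. Nor does the point call for modelling local recurrence: at the plan's rates 60 × 0.05 = 3 or 60 × 0.175 = 10.5 events are expected, which leaves little or no room for covariates.

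**What to change.** Prespecify an adjusted between-modality analysis of time to CTCAE toxicity as the main one. For example, use a Cox model with modality and a short list of covariates from the HRQoL model, such as age and ECE (which also represents chemotherapy). Limit the number of terms by the observed toxicity events, name the test (a likelihood-ratio test is preferable to Wald at these event counts), and report the HR with its 95% CI. Keep the unadjusted logrank as supportive. If events are too few for adjustment, report estimates with CIs and label the comparison descriptive. State residual confounding as a limitation.

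The cost is a few sentences of SAP text and the small power loss shown above if an adjusted factor is imbalanced but not prognostic. The team should also confirm that ECE and chemotherapy are recorded. The visit schedule in 5.1 and the data-flow text in 8.3 do not name them, but the case report forms are not in the document, and the HRQoL model already needs baseline clinical data.

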2.2 Secondary Objectives

- 2.2.1 Determine 2-year regional control, progression-free survival, metastasis-free survival, and overall survival
- 2.2.2 Determine differences between IMRT and proton therapy with respect to disease-related outcomes and toxicity/QOL

3 Study Design

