3.3 Secondary Study Endpoints

- 2 year regional control
- 2 year progression-free survival
- 2 year metastasis-free survival
- 2 year overall survival
- Differences in toxicity/QOL between IMRT and PBRT

4 Subject Selection and Withdrawal

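### The IMRT versus PBRT comparison of local recurrence rests on a logrank test with about 3 expected events; an estimated difference with its confidence interval, labelled descriptive, would answer objective 2.2.2 better

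*Combined protocol and SAP*

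**What the plan says.** Section 6, Data analysis plan, commits to the following: "We will compare the distributions of time to local recurrence and time to toxicity between strata by the logrank test". No expected event count, error rate, sidedness or power is given for that test, and no rule for interpreting it.

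The sizes are set in the same section: "A total of 60 patients will be accrued over a total of 1.0 year", and "We anticipate enrolling approximately 30 subjects in each stratum". The split follows insurance approval, not randomization, and the sample size section adds that "this study will not obligate 1:1 IMRT:PBRT". That section also gives the planning rates of two-year local failure (both percentages): "assuming a null rate of 5% and an alternative rate of 17.5". They belong to a one-tailed exact binomial test at 10%, with stated power of 78% with 30 patients per stratum. The only other power statement concerns the HRQoL *t* test.

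On scope, objective 2.2.2 reads "Determine differences between IMRT and proton therapy with respect to disease-related outcomes and toxicity/QOL". The matching item in the endpoint list, section 3.3, is narrower: "Differences in toxicity/QOL between IMRT and PBRT".

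**The concern.** Objective 2.2.2 asks how the two modalities differ in disease outcome. For local recurrence, the only between-stratum result the plan will produce is a logrank p-value, and the planning rate implies very few events to support it. A non-significant result would be the likely outcome whether or not the modalities differ by a clinically relevant amount, and a p-value alone does not show the reader how large a difference remains possible.

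Two features of the text make this easier to miss. The 78% power statement is phrased per stratum and speaks of detecting a difference, so it can be taken as covering the modality comparison. And sections 2.2.2 and 3.3 do not match on whether disease outcomes by modality are an endpoint at all.

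**Working it through.** **Inputs from the documents.** 60 patients, about 30 per stratum, 1:1 not required (section 6). Two-year local failure 5% (null) and 17.5% (alternative) (section 6, sample size). Local control of 97% with surgery alone (section 1).

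**Assumptions.** Two-sided 5% test, 30:30 unless stated, every patient followed for 24 months, no dropout. The documents fix none of these for the logrank test.

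**1. The plan's own power figure.** For n = 30, rejecting a 5% failure rate at 4 or more failures gives an exact type I error of 0.061 and power of 0.795 at 17.5%, within two points of the stated 78%. (Rejecting at 3 or more would give a type I error of 0.188, above the 10% allowed.) So the 78% describes one stratum tested against a fixed 5%. Read as a two-sample comparison of 5% and 17.5% at one-sided 10%, power is about 0.60.

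**2. Expected events.**
- Both strata at 5%: 60 × 0.05 = 3.0.
- Both at the 3% failure seen with surgery alone: 60 × 0.03 = 1.8.
- One stratum at 5%, the other at 17.5%: 30 × 0.05 + 30 × 0.175 = 6.75.

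With both at 5%, the binomial chance of 3 or fewer events is 0.647, and of 4 or more 0.353.

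**3. The most extreme split with 3 events.** The logrank statistic is z = (O − ΣE) / √ΣV, where at each event E = n1/n and V = n1·n2/n². With all 3 events in one stratum of 30:
- ΣE = 30/60 + 29/59 + 28/58 = 1.474
- ΣV = 900/3600 + 870/3481 + 840/3364 = 0.750
- z = (3 − 1.474)/√0.750 = 1.76, two-sided p = 0.078

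The exact (Fisher) p is 2 × C(30,3)/C(60,3) = 2 × 4060/34220 = 0.24. A 2-1 split gives logrank p of 0.54 to 0.57, depending on the order of events.

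**4. Where rejection becomes possible.** These cases place all events in one stratum (the smaller one where sizes differ):

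| Strata | Events | Logrank p (two-sided) | Fisher p |
|---|---|---|---|
| 30:30 | 4-0 | 0.040 | 0.11 |
| 26:34 | 3-0 | 0.043 | 0.076 |
| 20:40 | 3-0 | 0.012 | 0.033 |

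The 3-0 split at 30:30 also gives a one-sided p of 0.039.

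**5. Power by simulation** (exponential times, 24 months):

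| True two-year failure | Rejection, two-sided 5% |
|---|---|
| 5% v 5% | about 3% |
| 2.5% v 7.5% | about 9% |
| 5% v 17.5% | about 35% |

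For 5% against 17.5%, power is 49% at two-sided 10% and 63% at one-sided 10%. The hazard ratio for that contrast is ln(0.825)/ln(0.95) = 3.75. Schoenfeld's formula needs 18 events for 80% power at two-sided 5%, against 6.75 expected.

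**6. What an interval would show.** Suppose 2/30 against 1/30 fail. The stratum rates are 6.7% (exact 95% CI 0.8 to 22.1) and 3.3% (0.1 to 17.2). The difference is 3.3 points, Newcombe 95% CI −10.8 to +18.2.

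**The case against.** The strongest reply is that this is a declared secondary comparison on which no decision depends. The interim safety rule uses the overall hazard, and the sample size section says an uneven split will not impede the primary objective. That stands, and it limits the importance of the point.

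It can also be said that intervals are partly planned already. The synopsis stratifies the analysis by type of RT and promises Kaplan-Meier curves and exact 95% intervals for two-year control (worded there as locoregional). This stands too. What is missing is an estimate of the between-stratum difference with its own interval.

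A reader might infer more than the documents support:
- **That the test can never reach significance.** This holds only for exactly 3 events (or fewer), strata close to 30:30 and a two-sided 5% level. It fails in the cases in step 4. Three events is also the expectation when both strata are at 5%, where not rejecting is correct. At 5% against 17.5%, the chance of 3 or fewer events is only about 8%; power is low, but rejection is possible.
- **That the test rejects too often.** A 4-0 rejection is fragile beside its exact p of 0.11, but with both strata at 5% the overall rejection rate is about 3%, which is conservative.
- **That a null result will be reported as no difference, or used to choose a modality.** Nothing says so. The introduction's remark about helping define the standard modality concerns patient-reported toxicity and quality of life, not local recurrence.
- **That the few-events argument covers time to toxicity**, which shares the quoted sentence. It does not.
- **That 2.2.2 and 3.3 contradict each other on the test.** Section 3.3 is shorter than the objectives and the analysis plan. That is an omission to reconcile, not evidence that the test was meant to be excluded.

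**Conclusion.** The point holds in limited form. At the planning rate about 3 local recurrences are expected. Under 30:30 strata, a two-sided 5% test and complete 24-month follow-up, the logrank comparison has about 35% power for 5% against 17.5% and about 9% for 2.5% against 7.5%. Relaxing the level to one-sided 10% raises the former to 63%, still below the 78% that the plan quotes for a different test. Dropout, for which no rate is given, would reduce the event count further.

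A non-significant p-value would therefore say little about objective 2.2.2, and an interval would show plainly how much remains unknown. This is a minor improvement to a secondary objective. It does not touch the primary estimates, the interim safety test or the toxicity and HRQoL comparisons.

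**What to change.** In section 6, Data analysis plan, for local recurrence only:
- State that the IMRT versus PBRT comparison is descriptive.
- Report two-year local failure in each stratum with its exact 95% CI, and the between-stratum difference with a 95% CI, for example by Newcombe's method.
- Base any conclusion on these in place of the logrank p-value, which is either dropped or kept as a supporting figure.
- Note beside the 78% power statement that it refers to each stratum tested against 5%, not to the comparison of strata.

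Leave the logrank test for time to toxicity as it is. Bring sections 2.2.2 and 3.3 into line, so that disease outcomes by modality either appear in both (as descriptive) or in neither.

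The cost is wording only, with no new data or patients. What is lost is one p-value of low information, dropped or demoted.

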This study is the first of its kind exploring such an approach in this patient population, and if high rates of locoregional control are obtained with less toxicity, it would potentially represent a paradigm shift in how patients with locally-advanced oropharynx cancer are managed.

This study will allow for RT to be given with either IMRT or PBRT (decision to treat with IMRT vs. PBRT not based on clinical features, but rather, insurance approval). Our initial patient experience with pencil-beam proton therapy reveals significant decreases in doses to critical organs at risk with no differences in coverage of radiation dose to at-risk tumor sites. For example, doses delivered to the oral cavity have consistently been reduced 10-fold with proton therapy compared to IMRT, with the first 2 patients reporting no changes in taste sensation near the end of their proton course.

We expect robust accrual to this protocol, as the Department of Otolaryngology performs over 800 resections annually for head and neck cancer, and the Department of Radiation Oncology treats over 200 patients annually with head and neck cancer. The majority of the patients receiving radiation do so after TORS and SND. We expect that approximately 150 patients annually will be eligible to participate on this study. Of these patients, based on current experience, approximately half will end up receiving IMRT, and half receiving PBRT, based solely on patient insurance carrier approval/denial of request for proton therapy (patient are not randomized to IMRT vs. PBRT).

We will prospectively administer patient-reported questionnaires to evaluate toxicity and quality of life to all patients, representing the first direct comparison of photon versus proton therapy for patients receiving head and neck radiation, and may potentially help define the standard RT modality for such patients.

2 Study Objectives

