2.1 Primary Objective

- 2.1.1 Determine 2-year local control with omission of primary tumor bed RT.
- 2.1.2 Determine 2-year toxicity, as measured per CTCAE, version 4.0 and patient-reported HRQoL.

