5.1 General study design

Sixty subjects will be enrolled on this single-arm Phase II study investigating the efficacy and safety of omitting postoperative RT to the primary tumor site in patients with locally-advanced (stage III or IVa) HPV+ oropharynx cancer who undergo TORS resection and neck dissection. Patients will be required to have a negative surgical margin (defined as 2mm or greater) after

resection of the primary site for a pathologic T1 or T2 cancer, with no evidence of perineural invasion.

Patients will be treated to the regional nodes, per current clinical standards, to a total dose of 60-66 Gy over 30-33 fractions, as determined by current clinical guidelines for postoperative radiation therapy (10-12). Both IMRT and PBRT will be allowed. Platinum-based chemotherapy will be delivered concurrently with RT, as clinically indicated for ECE (10-12).

Clinical, toxicity and QOL evaluations will be obtained at baseline (prior to RT), and completion of RT, and then at approximately 3, 6, 12, 18 and 24 months after completion of RT, during routine clinical follow-up appointments. Routine clinical follow-up will continue after this time point, at the discretion of the treating physicians.

Local recurrence will be defined as biopsy-proven recurrent squamous cell carcinoma at the original, primary tumor site.

Study Visit Schedule & Procedures

	*Baseline	End RT	**3mo. post RT	**6mo. post RT	**12mo. post RT	**18mo. post RT	**24mo. post RT
ICF	x						
Eligibility	x						
PE	x	x	x	x	x	x	x
QOL form	x	x	x	x	x	x	x
Tox. Assessment		x	x	x	x	x	x

*prior to RT ** approximately

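### As listed, the HRQoL mixed model omits the pre-RT HRQoL score and any visit terms, so the secondary IMRT-PBRT comparison loses precision and can carry over a baseline difference

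*Combined protocol and SAP*

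**What the plan says.** The comparison of modalities is secondary objective 2.2.2: "Determine differences between IMRT and proton therapy with respect to disease-related outcomes and toxicity/QOL". Section 6 (Sample size justification) confirms its rank: "The comparison of IMRT to PBRT is a secondary objective of the study".

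The model is given in one sentence of Section 6 (Data analysis plan): "We will estimate mixed linear models predicting HRQoL from treatment stratum, demographic and baseline clinical criteria". The next sentence gives the reason for the covariates: "It is necessary to adjust for these factors to reduce potential confounding bias, as the treatments will not be randomized". The synopsis adds only that linear models will compare mean HRQoL between strata.

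The score is measured before treatment. Section 5.1 states: "Clinical, toxicity and QOL evaluations will be obtained at baseline (prior to RT". Section 6 repeats the schedule: "HRQoL evaluations will be obtained at baseline and completion of RT, and then approximately at 3, 6, 12, 18 and 24 months after completion of" (radiation therapy). The visit table in Section 5.1 and the follow-up paragraph in Section 8.3 agree. That makes one baseline and six later assessments.

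On allocation, the background in Section 1 describes the "decision to treat with IMRT vs. PBRT not based on clinical features, but rather, insurance approval".

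Nowhere do the documents name the baseline HRQoL score as a covariate, specify a change score, or list a visit or stratum-by-visit term. The clinical criteria at baseline that will enter the model are not defined.

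**The concern.** The plan itself calls adjustment necessary because modality is not randomized. The pre-treatment value of the outcome is the obvious variable to adjust for, and it is already collected. Allocation by insurance approval limits selection by the clinician, but it does not make the two strata alike in HRQoL before RT. Demographic covariates may capture part of any difference, but they do not replace the score itself.

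Two things are at stake in the secondary comparison. Residual variance that the baseline score would explain stays in the error term. And a baseline difference between strata that the planned covariates miss can be read as an effect of modality. The missing visit terms add to this: with six post-RT assessments and only a stratum main effect, the model does not say which contrast over time is being estimated.

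**Working it through.** **Inputs from Section 6.** 30 patients per stratum, two-sided Student t test, type I error 5%, power 90%, effect size 0.86 SD.

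**Assumptions, not in the documents.** Correlation r between the baseline score and a later visit of 0.3, 0.5 or 0.7; a baseline difference of 0.3 SD where bias is shown; equal SD at both times; one follow-up visit; complete data; none of the planned covariates applied. Triplets below are in the order r = 0.3/0.5/0.7.

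**1. The plan's own figure.** With n = 30 per stratum, the noncentrality is d × √(n/2) = 0.86 × √15 = 3.33 on 58 df. Power is 90.6%, and the effect detectable with exactly 90% power is 0.851 SD. The statement in the plan reproduces.

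**2. Precision with the baseline score as covariate.** The residual SD is √(1 − r²) = 0.954/0.866/0.714, with 57 df. The 90% detectable effect in residual SD units is 0.8514, so:
- r = 0.3: 0.8514 × 0.954 = 0.81 SD
- r = 0.5: 0.8514 × 0.866 = 0.74 SD
- r = 0.7: 0.8514 × 0.714 = 0.61 SD

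Allowing for the estimated slope changes these only slightly (0.819/0.744/0.613). In a six-visit model with stratum-by-visit terms and one baseline slope (compound symmetry), the variance of the 24-month contrast is 0.915/0.755/0.514 of its unadjusted value. The one-visit formula 1 − r² gives 0.91/0.75/0.51, so it is a fair guide.

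**3. Carry-over of a 0.3 SD baseline difference when there is no modality effect.** Two alternative scenarios:

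| Scenario and analysis | Bias (SD) | Type I error (nominal 5%) |
|---|---|---|
| Fading (r × 0.3 at follow-up), unadjusted | 0.09/0.15/0.21 | 6.4/8.8/12.6% |
| Fading, baseline as covariate | 0 | about 5% |
| Fading, change from baseline | −0.21/−0.15/−0.09 | 10.6/8.6/7.2% |
| Stable (0.3 at every visit), unadjusted | 0.30 | about 21% |
| Stable, baseline as covariate: 0.3 × (1 − r) | 0.21/0.15/0.09 | about 13/10/8% |
| Stable, change from baseline | 0 | about 5% |

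The unadjusted rows come from the noncentral t. The other rows come from simulation with 100,000 trials per scenario.

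**4. Baseline kept as one of the repeated outcomes.** With only a stratum main effect and compound symmetry, each of the seven assessments has weight 1/7. The stratum coefficient then recovers 6/7 = 0.857 of a constant post-RT effect. A fading 0.3 SD difference contributes 0.3 × (1 + 6r)/7 = 0.12/0.17/0.22 SD, and a stable one contributes 0.30 SD. This reading averages the baseline difference into the treatment effect and does not remove it.

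**5. Change from baseline.** The SD is √(2(1 − r)), so the detectable effect is 0.851 × √(2(1 − r)) = 1.01/0.85/0.66 SD. That is less precise than the covariate model at every r shown.

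**The case against.** The strongest reply is that the sentence is brief and may have been meant to cover the score. The baseline clinical criteria are undefined and could include it. Section 5.1 does name QOL separately from clinical evaluations, but that wording describes visit assessments and not model terms. The HRQoL schedule, baseline included, stands directly before the model sentence, so baseline might be one of the repeated outcomes. This stands to the extent that a reader may not conclude that the plan deliberately excludes the score. It does not rescue the model, because the outcome-row reading needs visit and stratum-by-visit terms, and neither is listed.

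Second, the bias is hypothetical. No document reports a baseline difference or a correlation, modality is said not to follow clinical features, and demographic covariates are already planned. This stands too: the figures show what could happen, not that the strata differ.

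Third, 0.85 SD belongs to an unadjusted one-visit t test and not to the planned covariate-adjusted mixed model. That is correct. Planned covariates that share variance with the baseline score would shrink both the gain and the bias shown, and at r = 0.3 the gain is only about 5% to begin with (0.851 to 0.812 SD).

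A reader might also infer that HRQoL must be contrasted at 24 months, since objective 2.1.2 reads "Determine 2-year toxicity, as measured per CTCAE, version 4.0 and patient-reported HRQoL". That is a different, primary objective. Sections 2.2 and 3.3 set no time point for the modality comparison.

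**Conclusion.** The point holds as a gap in a secondary analysis. As listed, the model does not use the pre-RT HRQoL score and has no visit structure. On the plain reading it gives up precision (0.85 against 0.81/0.74/0.61 SD) and can carry over a baseline difference that the planned covariates do not capture. These sizes rest on the assumed correlations, the assumed 0.3 SD difference, one visit and complete data.

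Three stronger conclusions are not supported. A reader might take 0.09/0.15/0.21 SD as the most that a 0.3 SD difference can do. It is only the fading case: a stable difference gives 0.30 SD, and neither scenario is an upper bound. A reader might infer that the power statement is wrong, but it reproduces for the test it names. A reader might expect the added covariate to settle the confounding, but in the stable case 0.21/0.15/0.09 SD of bias remains.

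The primary local control endpoint is unaffected. The change is worth making because the data are already collected, and a model fixed in advance prevents a later choice among unadjusted, adjusted and change-score results.

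**What to change.** In Section 6 (Data analysis plan), state that post-RT HRQoL will be modelled with the pre-RT HRQoL score as a covariate, categorical visit and stratum-by-visit terms, and the planned demographic and clinical covariates. Report a change-from-baseline analysis as sensitivity only, since it is unbiased in the stable case where the covariate model is not. The time point of the contrast is the sponsor's choice.

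This takes two or three sentences and no new visits or data. The model gains about 11 fixed-effect parameters (1 baseline + 5 visit + 5 stratum-by-visit). Patients without a baseline form drop out of the covariate model unless baseline is kept in the outcome vector alongside those visit terms. If 10% lack the form (30 × 0.9 = 27 per stratum), the detectable effect is 0.86/0.78/0.64 SD, so the gain at r = 0.3 is lost.
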